9.3.1 Dose Modifications

3 litre PEX if \leq 100Kg and 4 litre PEX if >100Kg

.

9.4 Subsequent assessments and procedures

9.4.1 Visit schedule and assessments

A schedule of all trial assessments and procedures is set-out in **Appendix 3**.

Day 1- 5

- eligibility check pre PEX if randomised to PEX
- Vitals pre and post PEX (temperature, blood pressure, pulse, respiratory rate and oxygen saturation level) or once daily
- Plasma exchange if randomised to PEX
- assessment of compliance with PEX
- general physical examination
- recording of relevant concomitant medications eg start stop dates of antibiotics, noradrenaline
- Daily routine bloods (FBC, renal, liver function and coagulation screen with fibrinogen)
- Inflammatory markers on D1,D3 &D5 (LDH, CRP, D dimer, ferritin)
- Citrated plasma and serum samples pre and post PEX, or daily for those randomised to SOC to save for VWD screen, ADAMTS13 activity, COVID-19 serology, and multiplex inflammatory markers related to ILs cytokines, interferons, and vascular markers of endothelial injury. Spare samples can be used for COVID-19 related research as authorised by the trial team
- Respiratory parameters: Oxygen requirement, respiratory rate, type of ventilator support-as part of standard of care assessment
- Echocardiogram on D1
- Troponin and BNP on D1
- adverse event collection
- Reactions to Plasma exchange: graded 1-4
- Complications related to central vascath
- Need for antibiotics
- Deterioration requiring ventilation
- Arterial or venous thrombotic event

Reassessment (Day 5-7)

Review of clinical and laboratory parameters by trial team. Consideration of further 5 day block of PEX if clinical and biochemical improvement following initial 5-day block but persistent pro-thrombotic phenotype

*If a patient has a second 5 days of PEX started-follow instructions for day 1-5 above

Follow up Day 6 - 28*

- Vitals (temperature, blood pressure, pulse, respiratory rate)
- general physical examination-weekly
- recording of concomitant medications-related to antibiotics, new cardiac medication, but not all the routine medicines re SOC and not including PRN medications.
- Daily routine bloods (FBC, renal, liver function and coagulation screen with fibrinogen)
- Inflammatory markers, at least 3 x/week (LDH, CRP, D dimer, ferritin)
- Citrated plasma and serum samples taken at least weekly to 28 days to save for VWD screen, ADAMTS 13 activity, COVID-19 serology, and multiplex inflammatory markers related to ILs cytokines, interferons, and vascular markers of endothelial injury. Spare samples can be used for COVID-19 related research as authorised by the trial team
- Respiratory parameters
- Echocardiography D7
- Troponin/BNP weekly D7, D14, D21, D28
- Adverse event collection
- Need for antibiotics
- Deterioration requiring ventilation
- Arterial or venous thrombotic event

End of study Day 28

- 28 day mortality and outcomes
- Echocardiogram, if available, D28

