3.2 Pilot data

Levels of protein S, protein C, antithrombin, Factor VIII, vWf, platelet counts, and ADAMTS-13 activity were measured in patients admitted to the ICU for respiratory support. Levels of protein S, protein C, antithrombin, and ADAMTS-13 activity were within the normal range. In contrast, levels of factor VIII and VWF were significantly elevated among critically ill patients with COVID-19.

A total of 6 patients at UCLH with COVID-19 requiring advanced respiratory support with features of TMA were consented to undergo PEX. A total of 5 days single volume PEX was conducted, and patients clinical and biochemical data compared to matched controls. Matched controls included patients who were eligible for PEX but did not consent (n=1) or did not receive PEX due to limitations on staff resource (n=7).

There were no reported adverse events associated with PEX.

The pertinent findings were :

- no thrombotic events during the duration of PEX
- decrease in the VWF/ADAMTS 13 ratio throughout the period of treatment
- decrease in inflammatory markers, in particular, D Dimers, ferritin and LDH
- increase in lymphocyte count in all patients which was sustained after the PEX course was completed
- increase in median PaO₂:FiO₂ ratio from the beginning to the end of the PEX period
- No deterioration to acute kidney injury:
- Stable cardiac function as assessed by echocardiography

4 Assessment and management of risk

1. Central vascath insertion:

There is a risk of pain, infection and bleeding or thrombosis with central vascath insertion. All the central lines are put in by a defined trained group within the trust i.e. ICU/anaesthetics or interventional radiology. Patients with severe COVID-19 infection are likely to need central line access e.g. PICC/Central line. While these lines are not suitable for PEX, central venous access is common in COVID-19 patients in ICU. Patients will be monitored frequently for infections, bleeding or thrombosis

2: PEX

- A. Reaction to plasma: There is a risk of infusional and allergic reactions and rarely anaphylaxis with the use of Octaplas. This is considerably reduced with the use of Octaplas compared to standard fresh frozen plasma (FFP) Reactions grade 1-3 are amenable to standard therapy including antihistamine, hydrocortisone and paracetamol. If a patient experiences symptoms of anaphylaxis, treatment would be stopped immediately.

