- B. Citrate reactions: Some patients treated with PEX present with features of hypocalcaemia (fatigue, paraesthesia, tremor, and hypocalcemia). This is treated with calcium boluses, but offset by a calcium infusion throughout PEX.
- C. Risk of viral transmission: Standard measures to prevent infections resulting from the use of medical products prepared from human blood or plasma include selection of donors, screening of individual donations and plasma pool for specific markers of infection and the inclusion of effective manufacturing steps for the inactivation/removal of viruses. When medicinal products prepared from human blood or plasma are administered, the possibility of transmitting infective agents cannot be totally excluded. However Octaplas LG undergoes a number of additional pathogen inactivation steps and is considered very safe.

The table below summarises the risks, frequencies and mitigations of the IMP(s) and NIMP(s) (delete NIMP if it is not applicable)

Name of IMP(s) / NIMP	Potential risk	Risk Frequency	Risk Management
Octaplas	-Reactions to plasma - -Pathogen transmission	-Severe reactions- grade 4- anaphylaxis <1% -Due to nanofiltration and S/D processing, this is the safest and most effective plasma available	-Any reactions treated with antihistamine, paracetamol and /or hydrocortisone -PEX would be stopped if any severe reaction/anaphylaxis -routine viruses are checked pre PEX.
PEX procedure	Citrate toxicity	10-20% of procedures	IV calcium is run during PEX and added boluses given if required

Vascath insertion	Infection, bleeding, thrombosis	Approx. 10%	Lines are changed weekly to reduce infection, intermediate LMWH given, reducing thrombosis. Bleeding rare as lines inserted by USS
-------------------	---------------------------------	-------------	--

Type A = No higher than the risk of standard medical care

5 Objectives

The rationale of this study is to compare outcomes of patients receiving PEX to those who do not. We hope to ascertain if PEX provides a clinical benefit to expand its use nationally and internationally, as there is currently no treatment which improves the morbidity and mortality of patients with severe COVID-19.

Primary objectives:

To compare reduction in inflammatory markers between Plasma Exchange (PEX) and control groups in patients with severe COVID

Secondary objectives:

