10.5 Serious Adverse Events which do not require immediate reporting

SAEs associated with COVID-19 disease do not require recording in the CRF, SAE Recording Log or SAE Reporting Form. However, if the relationship between the IMP and an SAE cannot be ruled out the SAE must be recorded and reported to Sponsor as detailed above.

There is high rate of expected deterioration in this group of patients. Anticipated adverse events/interventions associated with COVID-19 infection which are not required to be captured as an SAE/AE include:

- abnormal pathology results from presentation (including inflammatory markers related to a hyperinflammatory response)
- secondary infection
- renal failure
- cardiac disease e.g. arrhythmias, right heart failure
- intubation and ventilation
- VTE/arterial thrombosis
- end organ damage developing either biochemical e.g. AKI, liver impairment or clinical e.g. Intubation, thrombosis (either venous or arterial such as stroke)
- death from COVID19

This will be captured within the medical notes. These represent SAEs but are anticipated based on the natural history of the COVID-19 disease and so do not require immediate reporting. Mortality will be captured as an endpoint.

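### The vascath complication item stops with the PEX block, so later infections, bleeds or clots are not attributed to the line and PEX-arm harm may be understated

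*Combined protocol and SAP*

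**What the plan says.** **During a PEX block.** The Day 1-5 list in section 9.4.1 includes "Complications related to central vascath". A footnote extends that list: "If a patient has a second 5 days of PEX started-follow instructions for day 1-5 above". The second block is decided at the Day 5-7 reassessment: "Consideration of further 5 day block of PEX if clinical and biochemical improvement following initial 5-day block but persistent pro-thrombotic phenotype".

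**After the block.** The Day 6-28 list repeats most of the neighbouring items, including "Adverse event collection", "Need for antibiotics", deterioration to ventilation, and thrombotic events. It does not repeat the vascath item.

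**Line risk.** The risk table in section 4 gives infection, bleeding and thrombosis as the hazards of vascath insertion, at about 10% with no denominator. As mitigation it says "Lines are changed weekly to reduce infection". The text of section 4 adds "Patients will be monitored frequently for infections, bleeding or thrombosis", with no end day.

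**Adverse event rules.** Section 10.2 records adverse events from consent to the end of the trial, but keeps COVID-19-associated events out of the CRF. Section 10.5 lists COVID-19-associated events "which are not required to be captured as an SAE/AE include", and both secondary infection and venous or arterial thrombosis are on that list. The exemption is lifted when a relation between an SAE and the IMP cannot be ruled out. Section 7.1 defines the IMP as OctaplasLG.

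**The concern.** Dropping the plasma-reaction item after the block makes sense, since those reactions belong to the exchange itself. The same reasoning does not carry over to the line. Two of the three hazards named in section 4, infection and thrombosis, need not show themselves on an exchange day.

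Section 4 says that other central lines are not suitable for PEX, so the vascath is an invasive step that trial treatment imposes on one arm only. Section 5 says the trial is meant to inform wider use of PEX. A reader of the results will want to know what the line cost. If late complications are unlabelled, or are filed as COVID-19 events, the reported figure will be too low, and the error falls on the PEX arm.

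**Working it through.** The plan states no figure for late line complications, so there is none to reproduce. The check is a comparison of the two lists in 9.4.1, read against sections 10 and 12.1.2, followed by a short calculation for scale.

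**Step 1: what captures each hazard on Day 6-28, and does it name the line?**

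| Hazard | Routes left after the last block | Attributed to the line? | On the 10.5 list? |
|---|---|---|---|
| Thrombosis | Thrombotic-event item; secondary outcome 4 (imaging-documented, whole study period); general AE collection | No | Yes, but still counted as an outcome |
| Infection | General AE collection; antibiotic item | No; the antibiotic item asks for no cause | Yes, as secondary infection |
| Bleeding | General AE collection | No | No |

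**Step 2: does the 10.5 override rescue a late line infection?** Only in part. It refers to SAEs and to the IMP, which is plasma. An infection from the catheter is not obviously related to the plasma, so an investigator who reads 10.5 literally could class it as a COVID-19 secondary infection and leave it out of the CRF. Section 10.3.2 judges causality against the IMP or investigational treatment, which is wider, but 10.5 does not use that wording.

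**Step 3: how many days lack the item?**
- One block: 28 − 5 = 23 of 28 days.
- Two blocks: 28 − 10 = about 18 of 28 days.

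These are days without the prompt. They are not days at equal risk.

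**Step 4: scale.** Inputs are the approximate 10% from section 4, taken as per patient (assumption), and a PEX arm of 10 to 20 (section 2 gives a minimum of 20 and a maximum of 40 in total; randomisation is 1:1).
- Expected events in total: 10 × 0.10 = 1; 20 × 0.10 = 2.
- Chance of at least one: 1 − 0.9^10 = 65%; 1 − 0.9^20 = 88%.

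With an expected total of 1 or 2, losing a single event could change the report from some line complications to none. The documents give nothing from which to work out what share falls after Day 5.

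**The case against.** The strongest reply is that late events are already collected. Clots have an explicit item to Day 28 and are a secondary outcome, which an adverse event exemption cannot remove. Antibiotic use, temperature, a weekly examination and general adverse events all continue in follow-up, and Appendix 2 has an adverse event review through Day 28. The 10.5 exemption is limited to events associated with COVID-19, which a line infection is not by nature. The adverse event definition in 10.1 covers procedural interventions, and 10.4 sends all other SAEs to the CRF.

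Most of this stands. A reader might infer from the missing item that late line infections and clots are not collected at all; the documents do not support that. Nor does the lack of a vascath row in Appendix 3 help the argument, because that table has no row for adverse events or thrombotic events on any day.

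A reader might also reason that weekly line changes imply a 7-day dwell, so that 2/7 = 29% of the risk is lost and a true 10% would be read as 10% × 5/7 = about 7%. That does not hold either. No passage gives a removal day or says the line stays in for the Day 5-7 decision. A constant daily risk across bleeding, infection and thrombosis has no basis in the documents. And the sum treats every later event as lost, which the table above contradicts.

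The reply does not supply attribution. None of the continuing items asks about the line. A line clot counted in the thrombosis outcome is mixed with the clots that PEX is hypothesised to reduce, so the procedural harm cannot be separated out. Section 4 notes that central access is common in ICU patients with COVID-19, so comparing infections between arms would not isolate the vascath either.

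**Conclusion.** The point holds as one of attribution and possible misclassification. The vascath item is tied to PEX blocks and is not carried into follow-up. After the last block, no scheduled item links an infection, bleed or clot to the line, and 10.5 leaves room for a late line infection to be omitted from the CRF. A complication of a procedure needed only in the PEX arm could therefore be understated.

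The effect is limited to safety reporting; the primary outcome and its power are untouched. Its size cannot be derived. The 1 to 2 events in total rest on reading the section 4 figure as per patient, and the share after Day 5 is unknown. The conclusion does not depend on how long the line stays in.

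**What to change.** 1. Add the vascath complication item to the Day 6-28 list in 9.4.1 through Day 28, naming infection, bleeding and thrombosis. A matching row in Appendix 3 would keep the schedule consistent.
2. Record the dates of line insertion and removal, so that events can be placed relative to the time the line was in.
3. State in 10.5 that events related to the line or the procedure are not exempt from capture, alongside the existing override for the IMP.

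The second and third changes do not replace the first. Correcting 10.5 alone would still leave no prompt to ask about the line once the block is over.

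Cost: one extra CRF item, two dates per line, a little data entry at reviews already scheduled, and protocol wording. No added visits or tests.

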9.5 Laboratory Assessments and Procedures

Local laboratories

The following tests will be carried out at Local Laboratories:

Laboratory test	Parameters
BLOOD	
Haematology	leukocytes, erythrocytes, haemoglobin, haematocrit, mean corpuscular volume (MCV), mean corpuscular haemoglobin (MCH), platelets, neutrophils, eosinophils, basophils, lymphocytes, monocytes;

Serum chemistry	alanine transaminase (ALT), alkaline phosphatase, total bilirubin, creatinine, urea, potassium, sodium, albumin
Clotting screen	Prothrombin time, activated partial thromboplastin time, claus fibrinogen,
Inflammatory markers	C reactive protein (CRP), lactate dehydrogenase (LDH), D dimer, ferritin
Pregnancy test	Serum bhCG
Virology test	Covid 19 PCR, Covid 19 IgM and IgG, Hepatitis-B-virus surface antigen (HBsAg), anti-hepatitis C virus (anti-HCV) antibodies, immunodeficiency virus 1 and 2 (anti-HIV1/2) antibodies,
Cardiac markers	Troponin, BNP
Procoagulant markers	Factor VIII, VWF, ADAMTS-13 activity
Autoimmune screen	C3/C4 ANA ENA
Multiplex inflammatory markers	cytokines including interleukins, interferons, and vascular markers of endothelial injury 'cytokine storm'

Central laboratories

No central laboratory

Translational Research Samples

Citrated plasma and serum samples can be used for COVID-19 related translational research as authorised by the trial team. All data and samples will be available for COVID19 related research, to improve the understanding of the condition. This may be within the team/trust or in collaboration with external researchers. All data/samples in the latter situation will be anonymised.

The samples will be spun and stored in Special Coagulation Laboratory, [name]

Any analysis of samples needs a formal risk assessment re aerosol risk when spinning or as part of analysis and will only be undertaken following health and safety sign off within HSL/UCLH/UCL.

9.7 Assessment of IMP/NIMP compliance

PEX and NIMP will be administered as an inpatient IMP by trained apheresis staff as per Trust protocol so there will be no compliance issues.

9.8. Discontinuation/withdrawal of participants

Discontinuation of Trial Treatment for clinical reasons

A participant may be withdrawn from trial treatment whenever continued participation is no longer in the participant's best interests, but the reasons for doing so must be recorded. Reasons for discontinuing treatment may include

disease progression whilst on therapy

unacceptable toxicity: **anaphylaxis to plasma**

intercurrent illness which prevents further treatment

patients withdrawing consent to further trial treatment

Any alterations in the participant's condition which justifies the discontinuation of treatment in the site investigator's opinion

Persistent non-compliance to protocol requirements

The decision to withdraw a participant from treatment must be recorded in the CRF and medical notes, and the sponsor when required should be notified in writing.

In these cases participants remain within the trial for the purposes of follow-up for safety and or data analysis according to the treatment option to which they have been allocated

Participant withdrawal from trial treatment

If a participant expresses their wish to withdraw from trial treatment, sites should explain the importance of remaining on trial follow-up and seek permission to allow use of routine follow-up data to be used for trial purposes. The importance of safety follow-up should be emphasised to the participant in the Participant Information Sheet.

The decision of the participant to withdraw from treatment must be recorded in the CRF and medical notes.

The participant may withhold their reason for withdrawal however, if the participant gives a reason for their withdrawal, this should be recorded.

Withdrawal of Consent to Data Collection

If a participant explicitly states they do not wish to contribute further data to the trial their decision must be respected and recorded in the CRF and medical notes.

Loss to follow-up

If a participant moves from the area, every effort should be made for the participant to be followed up at another participating trial site and for this new site to take over the responsibility for the participant.

9.8 Replacements

Withdrawn participants would not be replaced

9.9 Stopping rules

The trial may be stopped before completion for the following reasons:

Anaphylaxis to plasma during PEX

On the recommendation of the TMG

On the recommendation of the sponsor and CI

9.10 Definition of End of Trial

The end of trial is day 28 of the last participant.

10 Recording and reporting of adverse events and reactions

Collection, recording and reporting of adverse events (including serious and non-serious events and reactions) to the sponsor will be completed according to the sponsor's SOP (INV/S05).

10.1 Definitions

Term	Definition
Adverse Event (AE)	
Any untoward medical occurrence in a patient or clinical trial participant administered a medicinal product and which does not necessarily have a causal relationship with this treatment.
 
Therefore an AE can be any unfavourable or unintended change in the structure (signs), function (symptoms) or chemistry (laboratory data) in a participant to whom an IMP or procedural intervention has been administered, including occurrences which are not necessarily caused by or related to that product.

Adverse Reaction (AR)	
Any untoward and unintended response in a participant to an investigational medicinal product which is related to any dose administered to that participant.
 
This includes medication errors, uses outside of protocol (including misuse and abuse of product)

Serious Adverse Event (SAE), Serious Adverse Reaction (SAR) or Unexpected Serious Adverse Reaction	
Any adverse event, adverse reaction or unexpected adverse reaction, respectively, that:
 
 • results in death, • is life-threatening*, • requires hospitalisation or prolongation of existing hospitalisation**,

	
 • results in persistent or significant disability or incapacity, or • consists of a congenital anomaly or birth defect 
*A life- threatening event, this refers to an event in which the participant was at risk of death at the time of the event; it does not refer to an event which hypothetically might have caused death if it were more severe.
 
** Hospitalisation is defined as an in-patient admission, regardless of length of stay. Hospitalisation for pre-existing conditions, including elective procedures do not constitute an SAE.
 
Some medical events may jeopardise the subject or may require an intervention to prevent one of the above characteristics/consequences. Such important medical events should also be considered as serious.
 
The term “severe” is often used to describe the intensity of an event or reaction (mild, moderate or severe) and should not be confused or interchanged with the term “serious”.

Suspected Unexpected Serious Adverse Reaction (SUSAR)	A serious adverse reaction, the nature, severity or outcome of which is not consistent with the Reference Safety Information.
Reference Safety Information (RSI)	A list of medical events that defines which reactions are expected for the IMP being administered to clinical trial subjects, and so do not require expedited reporting to the Competent Authority. It is contained in a specific section in the Summary of product characteristics (SmPC) or the Investigator Brochure (IB).

